Subsequent to the above-mentioned phase 1 study, a prospective longitudinal phase 2 study was initiated to evaluate the use of Gravid Ovipositing Sticky (GOS) trap and the NS1 testing system for surveillance of dengue virus transmission in urban Malaysia over a two-year period. The findings showed that dengue cases would occur lag one week after infected mosquitoes are obtained and will peak at lag of 2 to 3 weeks (30). These results showed that this proactive strategy is beneficial for dengue vector surveillance programme. The usage of the GOS trap which is simple to setup, cost effective (below USD 1 per trap) and environment friendly (i.e. use recyclable plastic materials) to capture *Ae. aegypti* followed by a rapid method of detecting of dengue virus using the NS1 dengue antigen kit has shown promising results. Control measures could be initiated when positive mosquitoes are detected, for example activity such as search and destroy breeding containers. This innovative usage of GOS trap coupled with NS1 detection in mosquito provides a comprehensive early warning and surveillance system that has the predictive capability for epidemic dengue.

6. Relevance to Government Policy, if any

This cluster randomised trial is expected to provide robust estimates of the intervention effects. A rigorous evaluation of these vector control interventions is vital to the development of an evidence-based control strategy and to help direct government resources in the right direction to reduce dengue epidemics.

7. Methodology

This is a community-based study assessing the knowledge, awareness and practice on dengue infection and its prevention. We choose PJU10 because it is the dengue 'hotspot' area according to local health council. We have identified a low-cost housing area with population of approximately 48700 people.

Sample size calculation:

Sample size for intervention trial:

To test for effectiveness of intervention in reducing dengue cases, on average, each housing unit will have 2% risk of dengue per year. A sample of 5710 unit (2855 per arm) will be required to achieve 80% power at alpha of 0.05 with the assumption of reduction in 50% of risk at the end of intervention. Eight apartments with 7979 residential units will be selected and randomised into intervention and control. Apartment will be the item of randomisation.

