All clusters in intervention arm will receive the GOS traps. A maximum of 21 traps will be set per apartment block, on every third floor. The traps will be monitored weekly and the abdomen of *Aedes* obtained will be tested for dengue virus using the NS1 antigen test kit. If positive search and destroy measures will be conducted by the community under the supervision of community leader and the health staff. To identify the mosquito which carries the virus, dengue NS1 antigen tests will be carried out from the head and thorax of the individual mosquitoes from positive pool of mosquitoes. For the control clusters, routine dengue control and surveillance will be carried out as per the current Ministry of Health control activity, where no traps will be set, and dengue control measure will be initiated when human cases are reported from the control group. Data collection will be conducted for 1 year and 6 months.

When a positive mosquito is obtained, flyers and banners will be distributed and hung to inform the residents of the presence of dengue transmission in the apartment block/apartment. Alternatively, the residents may also be approached house-to-house or an educational booth set up at strategic locations in the apartment to warn and educate the residents.

Phase III: Repeat of KAP questionnaire

The KAP questionnaire survey will be repeated 15 months after intervention in the intervention arm.

Phase IV: Statistical Analyses

Data of serologically confirmed dengue cases (by NS1 or IgM/IgG) from the eight residential blocks will be obtained from the Selangor State Health Department, Malaysia. It is mandatory for all hospitals and private practitioners to report cases to the Ministry of Health. The date of onset of case will be used for all data analyses.

For analysing the change in level of dengue KAP, the mean of the percentage score of the population for each domain (knowledge & attitude/practises) will be determined for the pre- and post-questionnaire. Then, paired t-test will be performed to determine the presence of significant changes in both means. A p-value of at most 0.05 indicates a significant change/improvement in the mean score (An increase in score percentage indicate a better outcome). Additionally, an individual percentage score of 80% and above indicates good knowledge/attitude/practice. Accordingly, chi-squared test will be used to determine the extent to which good knowledge is related to good attitudes/practises

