All statistical analyses will be done using weekly data and R programming language for statistical analysis (version 3.2.4) (30). The family of distributed lag non-linear models (DLNM), (*DLNM* package version 2.20), which can simultaneously analyse non-linear factor-response dependencies and delayed effects, and provides an estimate of the overall effect in the presence of delayed contributions will be utilised. For dengue cases and its relation to dengue-positive *Aedes* pool, the model to be used will be: `glm(case ~ cb.total_aedes + cb.ns1positive + ns(time, 3) + woy, family = quasipoisson, data)` where `woy` = week of the year. Both the *Ae. aegypti* / *Ae. albopictus* trapped per week and cases per week at each apartment will be analysed by generalised linear mixed model (GLMM). Zero inflation and Poisson distribution were incorporated in the analysis. Differences in numbers of *Ae. aegypti* and cases between blocks and between floors were tested with Tukey's contrasts at $P = 0.05$.

References

1. Gubler, D.J., and Clark, G.G. (1995). Dengue/dengue hemorrhagic fever: the emergence of a global health problem. *Emerg Infect Dis* 1, 55.
4. Faria NR, da Silva Azevedo RS, Kraemer MU, Souza R, Cunha MS, Hill SC, et al. (2016). Zika virus in the Americas: Early epidemiological and genetic findings. *Science* 352(6283):345-9.

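### The 80% power for 5710 housing units is unsupported: eight apartments are randomised, and no between-apartment variation or design effect is stated

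*Combined protocol and SAP*

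**What the plan says.** Section 7 (Methodology, sample size for intervention trial) assumes that "each housing unit will have 2% risk of dengue per year" and gives the size of the dengue-case comparison: "A sample of 5710 unit (2855 per arm) will be required to achieve 80% power at alpha of 0.05". The effect it assumes is a halving of that risk by the time the intervention ends. On the design it says: "Eight apartments with 7979 residential units will be selected and randomised into intervention and control. Apartment will be the item of randomisation".

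On timing, Phase II says "Data collection will be conducted for 1 year and 6 months" and Phase III says "The KAP questionnaire survey will be repeated 15 months after intervention in the intervention arm". Neither states how much of the 18 months follows the start of the intervention.

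Phase IV plans a generalised linear mixed model for weekly cases by apartment. It gives no variance assumption and makes no link to the sample size. Section 6 (Relevance to Government Policy) says: "This cluster randomised trial is expected to provide robust estimates of the intervention effects".

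**The concern.** The inputs to the 5710 figure (a risk, a relative reduction, alpha and power) are those of a trial that randomises housing units independently. This trial randomises apartments. Units in one apartment share mosquitoes, outbreaks and control measures, so the precision of the comparison depends on how much dengue risk differs between apartments and on having only eight of them. The plan attaches no such condition to its 80%.

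This is the only power statement for the dengue-case comparison, and section 6 wants the result to guide government resources. As written, a null result could be read as 80%-powered evidence of no effect when nothing in the plan shows that eight apartments give that power.

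**Working it through.** **Inputs from section 7.** Control risk 2% per unit per year; 50% reduction, so 1%; alpha 0.05 (taken as two-sided); power 80%; 2855 per arm; 8 apartments; 7979 units, so m = 7979/8 ≈ 997 per apartment and 3989.5 per arm.

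**Assumptions, because the plan does not give them.** Four equal apartments per arm; k over a range from 0 to 0.5, the same whatever the follow-up; at most one case counted per unit; a constant halving of risk over the period; a t-test on apartment-level rates with 6 df, which is not the planned mixed model.

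**1. The plan's own figure.** The two-proportion formula is n = [1.960·√(2·p̄(1−p̄)) + 0.842·√(p1(1−p1)+p2(1−p2))]² / (p1−p2)². With 0.02, 0.01 and p̄ = 0.015:

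n = [1.960·√0.02955 + 0.842·√0.0295]² / 0.0001 = 2319 per arm, or 2515 with continuity correction.

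The stated 2855 does not follow. It is on the high side: 2855 independent units per arm give 87.5% power. Unstated extras come close but not exactly: 2319/0.8 = 2899, 2319 × 1.2 = 2783, or 2849 at 85% power with continuity correction.

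**2. Room for clustering in 7979 units.**
- 12-month risk: 3989.5/2515 = 1.59 to 3989.5/2319 = 1.72. The ICC is (1.59−1)/996 ≈ 0.0006 to (1.72−1)/996 ≈ 0.0007. With k² = ICC·(1−p̄)/p̄ at p̄ = 1.5%, k is about 0.20–0.22.
- 18-month risk (3% vs 1.5%; n = 1534, or 1664 with correction): 3989.5/1664 = 2.40 to 3989.5/1534 = 2.60, so k is about 0.25–0.26 at p̄ = 2.25%.

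These limits use the normal approximation, which ignores that there are only eight apartments.

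**3. Cluster-level power on 6 df.** The variance of the difference is [p1(1−p1)/m + p2(1−p2)/m + k²(p1²+p2²)]/4. At 12 months and k = 0.25:

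(0.0295/997 + 0.0625 × 0.0005)/4 = 0.0000152, SE = 0.0039, 0.01/0.0039 = 2.56. Against a critical t of 2.447 on 6 df, power is 57.5%. The normal approximation would say 72.7%.

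At k = 0.20 the same formula gives 81% by the normal approximation but 66% on 6 df. This is why the headroom in step 2 overstates what the design tolerates.

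**4. Simulation.** Gamma-distributed apartment risks, binomial counts, 4 vs 4 apartments of 997 units, risk ratio 0.5. The ranges cover a t-test on raw rates and one on log((cases+0.5)/units).

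| k | 12 months (2%) | 15 months (2.5%) | 18 months (3%) |
|---|---|---|---|
| 0 | 86–87% | 92–93% | 96% |
| 0.1 | 81% | 88% | 92% |
| 0.25 | 58–59% | 63–64% | 66–68% |
| 0.5 | 26–28% | 27–29% | 28–30% |
| k at which power is about 80% | 0.11 | 0.16 | 0.18 |

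The 18-month column applies only if all 18 months are under intervention. With 5710 rather than 7979 units, power at k = 0 is 72–74% over 12 months and 88–89% over 18.

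**5. Risk ratio detectable with 80% power, 7979 units.**

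| k | 12 months | 18 months |
|---|---|---|
| 0 | 0.53 | 0.61 |
| 0.1 | 0.50 | 0.57 |
| 0.25 | 0.38–0.39 | 0.43–0.44 |
| 0.5 | 0.21 (log rates), 0.15 (raw) | 0.23 (log rates), 0.17 (raw) |

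**6. Unequal allocation.** With three apartments in one arm and five in the other, taken both ways, power is 74–81% at the 12-month limit (k = 0.11) and 74–82% at the 18-month limit (k = 0.18).

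**Scale of k.** At k = 0.11 and a mean risk of 2%, plus or minus two standard deviations of true apartment risk is 2% × (1 ± 0.22), about 1.6% to 2.4%. At k = 0.25 it is about 1% to 3%.

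**The case against.** The strongest reply is that the trial is larger than its calculation. The planned 7979 units are 40% above 5710 and 72% above the 4638 (2 × 2319) needed under independence. Eighteen months of cases add information beyond a yearly risk, and the mixed model can account for apartments. Under the assumptions above, power does exceed 80% when apartments are very alike: 81% at k = 0.1 over 12 months and 92% over 18. No document shows that k is larger, and the values 0.25 and 0.5 are illustrative. The plan also does not claim that clustering is irrelevant; it is silent.

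Much of this stands. It rules out saying that the trial is underpowered, and it means the k limits must carry their conditions: the t-test, the 4:4 split, equal sizes, and k unchanged with follow-up. It does not support the stated 80%. Nothing describes the surplus units as an allowance for clustering, and more units inside the same eight apartments add no degrees of freedom. A mixed model is a method of analysis; without a variance assumption it says nothing about power. The length of follow-up under intervention is itself not stated.

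The failure of 2855 to reproduce is a minor matter. An unstated loss allowance is possible, since section 7 adds 20% to its other samples, and the figure errs on the safe side.

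**Conclusion.** The concern holds. The 80% is stated for housing units in a trial that randomises eight apartments, and the quantity that mainly determines its power is not given. On the assumptions listed, power for a 50% reduction with 7979 units runs from 96% (k = 0, 18 months) to 26% (k = 0.5, 12 months). It reaches 80% only up to k of about 0.11, 0.16 or 0.18 for 12, 15 or 18 months under intervention. Power under the planned mixed model was not computed and may differ somewhat, but that model faces the same eight-apartment limit. The finding is that power is unknown and the stated figure is unsupported, not that the trial is too small. The derivation of 2855 is a separate traceability gap, not a shortfall.

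**What to change.** Replace the 5710-unit statement with a cluster-level calculation for the eight apartments and 7979 units:

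- Use the actual allocation and small-sample degrees of freedom, and name the test.
- State how much of the 18 months follows the start of the intervention, and show 12-month and 18-month risk side by side.
- Show k from 0 to 0.5. Inform it with past notified cases in these apartments if the State Health Department, already the source of case data, can supply them, and note that a k estimated from eight apartments is imprecise.
- Report both the power for a 50% reduction and the reduction detectable with 80% power.
- Give the derivation of 2855 or delete it.

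The cost is protocol wording and a short recalculation. The stated power becomes conditional and may look less favourable. Restating it requires no new apartments in itself, but it does not claim that eight are enough.

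### Eight apartments are randomised with no stated use of past dengue notifications, forgoing a cheap gain in precision for the case comparison

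*Combined protocol and SAP*

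**What the plan says.** Under Methodology, the sample size for the intervention trial assumes that "on average, each housing unit will have 2% risk of dengue per year", "with the assumption of reduction in 50% of risk at the end of intervention". It concludes that "A sample of 5710 unit (2855 per arm) will be required" for 80% power at alpha 0.05. The allocation is described in two sentences: "Eight apartments with 7979 residential units will be selected and randomised into intervention and control. Apartment will be the item of randomisation". No split, stratification, matching or other restriction is given.

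Under Phase IV, the outcome source is named: "Data of serologically confirmed dengue cases (by NS1 or IgM/IgG) from the eight residential blocks will be obtained from the Selangor State Health Department, Malaysia". No calendar window is attached to that extract. The 18-month data collection period is stated at the end of the first Phase II paragraph, on traps and control clusters.

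Two case models are named in Phase IV: a distributed lag model of cases on trap and NS1 terms, time and week of year, and a mixed model of weekly counts by apartment. Neither is described as having an arm term or a baseline case rate.

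The pre-intervention data that are planned (Phase I) are the KAP questionnaire and IgG/IgM serology in 500 people. Neither is carried into the case models.

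**The concern.** The apartment is the unit of randomisation, so the precision of the between-arm case comparison depends on how much dengue rates differ between apartments, and only eight are available. Units within an apartment add little once that variation matters, and longer follow-up does not remove it. The sample size paragraph counts units and gives no intracluster correlation, coefficient of variation or design effect.

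An apartment's own history is the obvious candidate for explaining part of that variation. Phase IV says that notification is mandatory and names the data holder, so earlier counts probably exist and would need no field work. A plan silent on them gives up precision for the 50% case reduction on which the sample size rests.

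**Working it through.** **1. The plan's own figure.** Inputs from the sample size paragraph: p1 = 0.02, p2 = 0.01, 80% power, alpha 0.05 (two-sided assumed; sidedness is not stated).

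n per arm = [1.96 x sqrt(2 x 0.015 x 0.985) + 0.842 x sqrt(0.02 x 0.98 + 0.01 x 0.99)]^2 / 0.01^2 = 2319, or 2515 with continuity correction.

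The stated 2855 is not reproduced; it would give 87.5% power. This is a side matter, but it shows that the calculation treats units as independent. With 7979/8 = 997 units per apartment and 4 x 997 = about 3990 per arm, the surplus absorbs a design effect of only 3990/2319 = 1.72, an intracluster correlation of about 0.72/996 = 0.0007.

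**2. Chance differences between arms.** Assumptions, none given in the documents: a 4:4 split and an SD s of apartment log-rates between 0.3 and 0.5. SE of the log rate ratio = s x sqrt(2/4); 95% range = exp(+/-1.96 x SE); chance of a twofold ratio in either direction = 2 x P(Z > 0.693/SE).

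| s | SE | 95% range, no effect | Twofold by chance |
|---|---|---|---|
| 0.3 | 0.212 | 0.66-1.52 | 0.1% |
| 0.4 | 0.283 | 0.57-1.74 | 1.4% |
| 0.5 | 0.354 | 0.50-2.00 | 5% |

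Poisson noise adds a little. Over 18 months each arm expects 7979/2 x 0.02 x 1.5 = about 120 cases, adding 2/120 to the variance; at s = 0.4 the range becomes 0.54-1.84.

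**3. Power without history.** With coefficient of variation k between apartments (assumed), m = 997 and a t test on 6 df:

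A = [p1(1-p1) + p2(1-p2)]/m + k^2 x (p1^2 + p2^2); noncentrality = (p1-p2)/sqrt(A/4).

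- k = 0: power 86% at one year, 96% at 18 months.
- k = 0.25: A = 0.0000296 + 0.0000313 = 0.0000608, noncentrality 2.56; power 57%, and 65% at 18 months.
- k = 0.5: A = 0.0000296 + 0.000125 = 0.000155, noncentrality 1.61; power 27%, and 29% at 18 months.

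**4. What history would buy.** Let rho be the correlation of past with follow-up apartment rates (assumed). Adjustment multiplies the error SD by sqrt(1 - rho^2) and moves from 6 to 5 df: t 2.57/2.45 = 1.05. Under unrestricted allocation there is a further penalty for chance imbalance in the covariate. A simulation of eight normal log-rates puts the total width ratio at about 1.15 when rho = 0.

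- Break-even, restricted: 1.05^2 x (1 - rho^2) = 1, rho = about 0.3.
- Break-even, unrestricted: 1.15^2 x (1 - rho^2) = 1, rho = about 0.5.
- At rho = 0.7, sqrt(0.51) = 0.714. Unrestricted: 1.15 x 0.714 = 0.82, so 18% narrower. Restricted: 1.05 x 0.714 = 0.75 by formula. The simulation gives 0.73, so 27% narrower, relative to an unadjusted analysis of the same restricted allocation (that analysis overstates its own error).

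One-year power with A multiplied by (1 - rho^2) and 5 df, which presumes a balanced covariate: at k = 0.25, 66% (rho 0.5) or 82% (rho 0.7); at k = 0.5, 33% or 44%.

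**5. Is 0.7 attainable?** At 2% per unit an apartment yields about 0.02 x 997 = 20 cases a year. With s = 0.3 and perfectly stable underlying rates, 12 months of history (20 cases) against 18 months of control follow-up (30 cases) caps rho at sqrt[0.09/(0.09 + 1/20) x 0.09/(0.09 + 1/30)] = 0.68. With 24 months (40 cases) the cap is 0.76. A longer history is therefore preferable, and 0.7 is optimistic if variation is at the low end.

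**The case against.** **Randomisation already deals with this.** In large part that stands. Chance differences between apartments are sampling error, and a valid apartment-level analysis carries them in its standard error. A reader might infer that without baseline data a trap effect cannot be separated from pre-existing differences. That is too strong: history improves precision and is not a condition for a valid comparison.

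**Hotspot selection.** The plan says "We choose PJU10 because it is the dengue 'hotspot' area according to local health council", from which a reader might infer bias or regression to the mean. The label applies to the area, and any such regression affects both concurrent arms. Nothing in the documents shows that apartments are at different outbreak phases. If they were, past rates would also predict follow-up less well.

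**Silence is not exclusion.** The case extract has no dates, so the plan does not say that earlier cases will be left out. Nor does it say that randomisation is unrestricted. Both are simply not specified, and the availability of older records is itself an inference.

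**The objective is entomological.** Objective (a) is worded as assessed by entomology surveys, and past cases do not help there. The point concerns the case reduction that drives the sample size.

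**Baseline serology exists.** It is a weak proxy. Spread evenly, 500/8 = 62.5 people per apartment gives an SE of sqrt(0.6 x 0.4/62.5) = 6 percentage points at the assumed 60% seroprevalence.

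**The mixed model handles clustering.** A random apartment effect would carry between-apartment variation but would not explain it, and no arm term is specified.

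**Conclusion.** The point holds as a loss of precision and power, not as bias. Eight apartments are randomised, and the plan states neither a restriction on the allocation nor any use of past notifications. The size depends on quantities the documents do not give: a 4:4 split, the between-apartment variation, and the correlation of past with future rates.

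A reader might infer that chance could readily imitate the halving sought. Over the assumed SD range a twofold ratio in either direction arises with probability 0.1% to 5% before Poisson noise, so this is uncommon. Failing to detect a true halving is the likelier outcome. Using history helps materially if the correlation is well above 0.3 (restricted allocation) or 0.5 (unrestricted). It does not restore the stated 80% power if apartments vary widely: at a coefficient of variation of 0.5, one-year power stays at 33% to 44% for correlations of 0.5 to 0.7. The change is worth making because it is cheap, but the small number of clusters remains the root limitation.

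**What to change.** 1. In the same request to the State Health Department, obtain confirmed cases by apartment for the 12 to 24 months before trap placement, preferably 24.
2. If allocation has not been done, use the past rate per unit to restrict it, for example by forming four rank-based pairs for balance only. If it has been done, keep it.
3. Write down the between-arm case analysis, which the plan does not yet define: an arm term, units as the denominator, and small-sample degrees of freedom at apartment level. Prespecify the log past rate per unit as the single apartment-level covariate, with a rule for an apartment with no past cases.
4. Break the pairs in the analysis. A pair-preserving analysis has 3 df (t 3.18 against 2.45, a critical value 30% larger) and should not be used.
5. Tabulate past rates by arm and report the unadjusted result beside the adjusted one. Under restricted allocation the unadjusted interval will be too wide when history is informative.

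Cost: one wider data request and a short SAP paragraph. If past rates prove uninformative, the interval is about 5% wider with restricted allocation, or about 15% wider on average with unrestricted allocation.

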Study Protocol with SAP

Title:

Cluster Randomized Controlled Trial: Efficacy of Gravid Oviposition Sticky Trap (GOS) and Dengue NS1 Antigen Rapid Diagnostic Test for Early Surveillance of Dengue Among Adult Aedes Mosquitoes to Reduce Dengue Outbreaks in PJU10, Damansara Damai, Selangor, Malaysia

Version date: 4 January 2019

Executive summary of study

Dengue, a serious vector-borne disease in Southeast Asian countries is fast emerging as a pandemic-prone disease globally. To add to the existing challenges, its mosquito vector, *Aedes aegypti* followed by *Aedes albopictus* are also vectors for other diseases such as chikungunya (outbreaks in 2008-2009) and Zika. In Malaysia, 120,000 cases of dengue were reported in 2015. In 2017 (until October), there were about 72,000 cases.

Surveillance are dependent on *Aedes* larval surveys and notifications of lab-confirmed human infections. However, there is no correlation between larval indices and cases of dengue. It is known that some asymptomatic people are infectious to mosquitoes. Therefore, the existing, reactive programme lacks sensitivity and is delayed, and has proven insufficient to stave off epidemics.

This current proposal unfolds a proactive and innovative paradigm shift. The creation of an in-house user-friendly technique to detect dengue virus in mosquitoes coupled with a community approach for early detection of dengue cases is an important and timely project. This proposed project will directly contribute to the Government's effort of reducing dengue as well as other vector borne diseases.

Traps will be set to collect *Aedes* mosquitoes weekly and virus will be detected in mosquitoes using dengue NS1 antigen test kit. When the positive mosquito is detected, the community will be alerted to conduct control measures (search & destroy). In the control areas, only ongoing dengue control and surveillance by the health authorities will be continued. KAP will be done before and after the intervention in intervention areas. If this study is successful, it has the potential to be a Model for Dengue Surveillance and Control and dossier to be submitted to WHO for adoption by Southeast Asian countries.

a) Research background

1. Problem Statement

Dengue is on the increase and the current surveillance and control measures are insufficient to control epidemics. The current method used is reactive rather than the proposed proactive measure.

2. Aim

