This trial aims to demonstrate community effectiveness of new proactive paradigm in reducing dengue epidemics. The main hypotheses are 1) This new paradigm (GOS trap and NS1 kit) will reduce dengue epidemics compared to the usual activities carried out by the Ministry of Health (including larval control and information and education material dissemination during outbreaks) as assessed through entomology surveys. 2) Community will be more receptive to this new surveillance activity as they will receive information of infected mosquitoes before dengue cases are reported, thus will be able to take informed steps to prevent themselves from being infected.

3. Objectives

- a) To determine new paradigm (GOS trap and NS1 kit) in reducing dengue epidemics compared to the usual activities carried out by the Ministry of Health (including larval control and information and education material dissemination during outbreaks) as assessed through entomology surveys.

- b) To determine whether the community will be more receptive towards this new surveillance activity as they will receive information of infected mosquitoes before dengue cases are reported.

4. Research Questions

Will the combination of setting up traps to collect *Aedes* mosquitoes coupled with detection of virus in the mosquitoes help to reduce/prevent impending dengue epidemics? Will this method be able to cover more premises compared to house to house larval surveys? Will this method reduce the cost of dengue surveillance and control compared to the current ongoing method?

5. Literature Review

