To test for effectiveness of intervention to improve knowledge, assuming the knowledge in control group is 50% and knowledge in intervention is 70%, total sample calculated to achieve 80% power at alpha of 0.05, is 208 (104 per arm). After inflation of 20% sample required is 250 (125 per arm).

Sample size calculation for survey/cross-sectional study:

For prevalence study (knowledge), assuming baseline knowledge in population is 50%, total sample calculated to achieve 80% power at alpha of 0.05, is 384. After inflation of 20% sample required is 460.

For sero-prevalence study (blood), assuming baseline dengue sero-prevalence in population is 60%, total sample calculated to achieve 80% power at alpha of 0.05, is 369. After inflation of 20% sample required is 443.

According to the sample size calculation, the final sample size will be 500. Therefore, 250 in intervention group and 250 in the non-intervention group (control).

Phase I: KAP Questionnaire survey and blood taking

Pre-tested questionnaires will be distributed to members of community who have given consent to participate in this study.

Inclusion criteria:

- 1) All men and women aged above 18 years, including pregnant women.
- 2) Able to give consent
- 3) Willing to participate in blood taking

Exclusion criteria:

- 1) Age below 18 years
- 2) Unable to give consent
- 3) Not willing to give blood

After the questionnaire survey, 3 ml of venous blood will be taken to analyse for seroprevalence of dengue infection (dengue IgG and IgM will be carried out).

Phase II: Placement of GOS mosquito trap in the intervention group

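### Knowledge is powered as control versus intervention (50% vs 70%), but the questionnaire is repeated only in the intervention arm and tested by a paired t-test, so the powered comparison has no control data at follow-up

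*Combined protocol and SAP*

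**What the plan says.** - **Section 7, Sample size calculation.** One calculation has the stated purpose "To test for effectiveness of intervention to improve knowledge". Its inputs are two arms: "assuming the knowledge in control group is 50% and knowledge in intervention is 70%, total sample calculated to achieve 80% power" at alpha 0.05. The result is 208 (104 per arm), or 250 (125 per arm) after 20% inflation. Two prevalence calculations follow, and the final survey sample is 500, with 250 in each arm.
- **Executive summary.** "KAP will be done before and after the intervention in intervention areas".
- **Phase III.** "The KAP questionnaire survey will be repeated 15 months after intervention in the intervention arm".
- **Phase IV.** Change in KAP is assessed on mean percentage scores before and after: "paired t-test will be performed to determine the presence of significant changes in both means". The reading rule is "A p-value of at most 0.05 indicates a significant change/improvement in the mean score". A chi-squared test relates good knowledge to good attitudes and practices; it does not compare arms. The distributed-lag and mixed models concern mosquito counts and dengue cases, not KAP.

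Nowhere is a follow-up questionnaire planned for control residents. Their baseline questionnaire serves the cross-sectional aims.

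**The concern.** The sample size, the data collection and the analysis describe three different things. The sample size compares two independent proportions between arms. The data collection gives follow-up scores in one arm. The analysis compares means within persons. Carried out exactly as written, the plan cannot perform the comparison for which it claims 80% power.

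The risk is a wrong claim about effectiveness. A change over 15 months in one arm mixes any intervention effect with everything else that happened. The plan itself names one such source: usual Ministry activity, "including larval control and information and education material dissemination during outbreaks". Answering the same questionnaire a second time is another. Apartments are randomised, which would deal with both, but a one-arm analysis makes no use of the randomisation. The dengue-case and entomological comparisons are not affected.

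**Working it through.** **1. Is the stated sample size really between-arm?**

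Inputs from section 7: p1 = 0.50, p2 = 0.70, power 80%, alpha 0.05 (two-sided assumed, as the plan does not say).

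n per arm = [1.960·√(2·0.6·0.4) + 0.842·√(0.25 + 0.21)]² / 0.20² = 93.0

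With continuity correction: (93.0/4)·[1 + √(1 + 4/(93.0·0.20))]² = 102.8, that is 103 per arm, against 104 stated. One-sided versions give 74 or 83 and do not fit. Inflation: 104 × 1.2 = 124.8, that is 125.

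The figure is therefore a two-sided, continuity-corrected calculation for two independent proportions. A paired t-test would need a mean change and the SD of the within-person change, and the plan gives neither.

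**2. What data will exist?**

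| | Baseline KAP | 15-month KAP |
|---|---|---|
| Intervention (250) | yes | yes |
| Control (250) | yes | none planned |

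The powered contrast needs both cells in the right-hand column.

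**3. How easily could the paired test mislead?**

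The plan gives no background drift and no SD, so this is an illustration on assumed values. There is no intervention effect, and the background gain is d, in SDs of the within-person change. Respondents are taken as independent. Rejection probability comes from the noncentral t with n − 1 df and noncentrality d·√n; for example, 0.20·√200 = 2.83. The 200 pairs stand for 250 less an assumed 20% loss.

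| d | 200 pairs | 250 pairs |
|---|---|---|
| 0 | 5% | 5% |
| 0.05 | 11% | 12% |
| 0.10 | 29% | 35% |
| 0.20 | 80% | 88% |
| 0.25 | 94% | 98% |

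**4. What would a control re-survey achieve?**

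Section 7 says "Eight apartments with 7979 residential units will be selected and randomised into intervention and control". Assume a 4:4 split, equal numbers per apartment (m), a t-test on apartment proportions (8 − 2 = 6 df) and the plan's 50% vs 70%, without baseline adjustment.

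Variance of the difference = (0.25 + 0.21)·[1 + (m − 1)·ICC] / (4m)

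Example, 250 per arm: m = 62.5 and ICC 0.02 give a design effect of 1 + 61.5·0.02 = 2.23, variance 0.46·2.23/250 = 0.00410, noncentrality 0.20/√0.00410 = 3.12 and power 74%.

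| ICC (assumed) | 250 per arm (m = 62.5) | 200 per arm (m = 50) |
|---|---|---|
| 0 | 97% | 93% |
| 0.01 | 86% | 81% |
| 0.02 | 74% | 70% |
| 0.05 | 49% | 47% |
| 0.10 | 31% | 30% |

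Power falls to 80% at an ICC of about 0.015 with 250 per arm and about 0.011 with 200.

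**The case against.** The mismatch itself is hard to dispute, so the case against concerns its weight.

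- **The calculation does not drive recruitment.** Its 250 is below the 460 needed for the knowledge prevalence aim, and 500 exceeds both. Deleting it would change nobody's enrolment. This is true, but it only shows that the minimum fix is cheap.
- **Between-arm knowledge is not a listed objective.** The objectives concern dengue epidemics and community receptiveness. Even so, section 7 opens by describing a study of knowledge, awareness and practice, and gives knowledge its own effectiveness test and power.
- **One-arm follow-up looks deliberate, and Phase IV speaks of change, not causation.** This is fair: two sections agree on it. But then the sample size paragraph is wrong as written, and a reader who puts its effectiveness wording beside the p-value rule will take a significant change as an effect.
- **The illustrations rest on assumed drift.** They do, and the defect does not depend on them. The 5% at zero drift also assumes independent respondents. If changes were correlated within four apartments of 62.5, the paired test would reject about 12% of the time at ICC 0.01 and 33% at ICC 0.05, with no average drift.
- **The power figures are for unadjusted proportions, not the baseline-adjusted scores recommended.** This is correct. They are a guide, and adjustment could improve on them.
- **The text never says that the same residents are re-surveyed.** Only the choice of a paired test implies it. The repeat-answering bias depends on that linkage.

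**Conclusion.** The concern holds. The 80% power for control 50% versus intervention 70% is a property the design does not have: there are no control observations at 15 months, and the planned test uses a different contrast and outcome scale. This follows from the text alone. The plan's arithmetic is not at fault, since 104 per arm reproduces to within one.

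The size of the possible error cannot be fixed from the documents. On the assumed drifts above, the chance of a significant result without any intervention effect runs from about 11% to 94% with 200 pairs. The figures for the control re-survey rest on the assumed 4:4 split, equal apartments and ICCs. The fault must be corrected for the knowledge claim.

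**What to change.** **Minimum, wording only.** Delete the between-arm power statement for knowledge. Describe the KAP result as an uncontrolled pre-post change in the intervention arm. State that a significant paired t-test will not be reported as evidence that the intervention improved knowledge. The price is a weaker KAP claim.

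**Preferred, where feasible.** In addition, repeat the same questionnaire at 15 months in the enrolled control residents who consent. Compare 15-month scores between arms, adjusted for baseline score, by a method suited to eight clusters, such as a t-test on baseline-adjusted apartment means or a permutation test over apartments. Restate power for that comparison over a range of ICCs.

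This means recontacting up to 250 people, with some lost, for one more questionnaire each. The documents reviewed do not show whether they agreed to a second contact, so a consent or ethics amendment may be needed. The comparison may still fall short of 80% power at an ICC of 0.02 or more. Control data not collected at 15 months cannot be recovered later, so the choice has to be made before then.
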